Results: Our results showed that Silodosin turned out to be better in expulsing stone as well as in producing lesser side effects and hence better safety profile than Tamsulosin. Silodosin showed greater stone expulsion rate with about 55 patients expulsing stone in less than 14 days in comparison to just about 5 patients on Tamsulosin. Similarly, patients on Silodosin, showed lesser side effects as compared to Tamsulosin. Nine patients on tamsulosin (60.0%) and six patients on silodosin (40.0%) developed orthostatic hypotension. Only a very tiny percentage of patients reported abnormal ejaculation; two individuals on tamsulosin (66.7%) and one patient on silodosin (33.3%). Another side effect that was identified involved headaches, seen by four patients on silodosin (44.4%) and five patients on tamsulosin (55.6%).

INTRODUCTION

Stone disease is one of the most frequent presentations in the field of urology. A large number of these patients arrive with ureteric stones(1). Globally, occurrence of stone formation is 10-12% for men and 6-8% for women. Its prevalence in Pakistan is approximately 16%. The disease's burden has increased in all age categories and both genders over the past 20 years(2). The incidence of urolithiasis in different age groups is 12.2% in the persons 20-29 year old, 29.6% in those who are 30-39-year-old, and 31.5% in 40–49-year-old patients(3).

Medical management ae well as surgical removal are various options available for treating ureteric stones as per American Urology Association (AUA) and European Association of Urology (EAU) guidelines. However, due to risks of surgical approaches there is always an attempt for treatment by using medical expulsive treatment (MET) for ureteric stones first keeping in view different parameters. According to European Association of Urology Guidelines (EAU), the ureteric stones less than 10 mm can be treated with MET(4). Medical expulsive therapy (MET) is a well-established treatment option for distal ureteric stones, despite a sharp increase in minimally invasive techniques(5). Stones smaller than 5 mm have passage rates ranging from 71% to 98%, while stones with size more than 5 mm had expulsion rates ranging from 25% to 53%(6).

Many factors affect stone removal and must be considered while selecting MET for stones like ureteric spasm, location, size, and number of stones and duration for which it is present and also the ureteric architecture etc(7).

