All things considered, the thorough examination of the exclusions, withdrawals, and reported adverse effects in the pooled analysis sheds light on the difficulties and conclusions that have been found in a number of research. It emphasizes how crucial it is to closely monitor participant outcomes and unfavorable occurrences in clinical research in order to guarantee the efficacy and safety of the medicines being studied(30).

The treatment for distal ureteral stones with size less than 10 mm with tamsulosin and silodosin has resulted in a high output rates of 57-64% and 80 - 84%, respectively, according to randomized controlled studies. Nonetheless, compared to other trials, the tamsulosin success rate in those investigations is somewhat lower (31). However, tamsulosin demonstrated an 86% success rate in a randomized controlled study with almost 3000 patients(32). Tamsulosin has a 67–90.7% success rate in treating distal ureteral stones, according to Tao

et al.'s meta-analysis.20 The current study's tamsulosin success rates align with some studies (33).

Similar to the current investigation, the comparable rates in the Imperatore et al. study were 82% and 88%, and in the Arda et al. study they were 72.4% and 78.6%. These investigations also revealed no discernible difference between tamsulosin and silodosin. However, only young/middle-aged men were included in this study, whereas both of other investigations included both men and women. This sums up the main distinction between prior studies and the present investigation (34).

Tamsulosin is used commonly in our population for MET however Silodosin, a newer drug, is not used frequently for this purpose and is still under research. Also, comparison of Silodosin and Tamsulosin has not been explored in our population earlier.

Rationale

The purpose of this study is to examine and compare the effectiveness of silodosin and tamsulosin in medical expulsive therapy (MET) in terms of the rate at which stones are expelled from the body, as well as the adverse effect profiles in our patient group.

OBJECTIVES:

To evaluate and compare the efficacy and safety of medical expulsive therapy containing tamsulosin and silodosin, specifically.

To compare the side effect profile of tamsulosin and silodosin when given for medical expulsive therapy.

HYPOTHESIS:

Null Hypothesis:

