It is hypothesized that efficacy and safety of medical expulsive therapy, containing tamsulosin and silodosin, is almost the same and silodosin can be used with the same efficacy for the treatment of lower urinary tract calculi.

Alternative Hypothesis:

Silodosin is better than Tamsulosin in efficacy and safety.

OPERATIONAL DEFINITIONS:

STONE CLEARANCE:

Stone clearance will be defined as no evidence of stone on follow up X-ray KUB imaging at 4 weeks .

ANCILLARY PROCEDURES:

Additional urological procedures needed to remove the same stone for which medical expulsive therapy was given if it fails to remove the stone completely.

SIDE EFFECTS:

Any undesirable effect noticed after prescription of the drug including but not limited to abnormal ejaculation, headache, orthostatic hypotension, backache and gastritis etc.

MATERIALS AND METHODS:

STUDY DESIGN:

Prospective randomized control trial.

STUDY SETTING:

Outpatient department of Sir Ganga Ram hospital, Lahore.

DURATION OF STUDY:

18 months.

DURATION OF TREATMENT:

Four weeks.

SAMPLE SIZE:

Using the open-epic software, the sample size was estimated. The minimum sample size that we require is 208 patients with ureteric stone who fulfil the inclusion criterion with 104 in one group receiving tamsulosin and 104 in silodosin group (1:1 ratio) with an inflation of 10 percent for estimated loss to follow up, with an anticipated expulsion rate ranging from 58-64 percent in tamsulosin group and 78-83 percent in silodosin group with a risk difference of 19 to achieve a power of 80 percent and a level of significance of 5 percent.

SAMPLING TECHNIQUE:

Patients visiting the outpatient department of Sir Ganga Ram hospital will be selected by simple random sampling, fulfilling the inclusion criteria.

SAMPLE SELECTION:

Adult male and female patients fulfilling the inclusion criteria will be assigned into two groups by random allotment, 1^{st} group will be given Tamsulosin and 2^{nd} group will be given Silodosin for four weeks.

INCLUSION CRITERIA:

Following factors make up the inclusion criteria for this study.

- Patients between ages 18 years 55 years.
- Solitary unilateral ureteral stone
- Stone sizes less than 10 mm measured on non-contrast computed tomography of kidney, ureter and bladder.
- Stones being treated primarily with medical expulsive therapy
- Radio opaque Stone

EXCLUSION CRITERIA:

The presence of following factors will exclude the patients from our study:

- Pregnancy
- Untreated UTI

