Data will be entered and analyzed on SPSS version 22. Percentages and frequencies will be calculated for the demographic variables of the patients. The comparison of the two groups will be made by using T- test. P-value of less than 0.05 will be considered significant and the power used will be 0.80.

RESULTS

Frequency and percentage of demographic data

Variables		Frequency	Percentage	
Gender	Male	105	58.7	
	Female	74	41.3	
Income	Less than	108	60.3	
status	50000			
	50000 -150000	69	38.5	
	Greater than	2	1.1	
	150000			
	Normal	166	92.7	
BMI	Obese	13	7.3	
	None	136	76.0	
Comorbidity	HTN	33	18.4	
	Diabetes	10	5.6	

This information sheds light on the sample population's health and demographic distribution, showing a preponderance of people with normal BMIs and lower income levels, as well as a significant percentage of people without comorbid diseases.

In our study there are total 179 patients out of which 74 are females (41.3%) and 105 males (58.7%).

The income, 108 people, or 60.3% of the total, make less than 50,000Rs in month. Just 2 members, or 1.1 percent, make more than 150,000 monthly, while 69 participants (38.5%) have monthly salaries between 50,000 and 150,000.

13 persons (7.3%) are classed as obese, while 166 people (92.7%) have a normal BMI. These numbers represent a sizable fraction of the sample. In terms of comorbidities, 136 individuals (76.0%) state they have no comorbid conditions. Of the people with comorbidities, 10 (5.6%) had diabetes, and 33 (18.4%) had hypertension (HTN).

[figure not shown]

Figure 1: Pie chart of patients using Silodosin and Tamsulosin (Medicine Advised)

Use of medicine (Figure 1)

Tamsulosin and Silodosin, the two drugs prescribed to a group of patients, are distributed as shown in the pie chart. Of the patients, 43% were advised to take Tamsulosin, which is shown as the blue section on the chart. And (57%) of the patients were advised to take silodosin, as shown by the red segment.

Table2: Patient demographic characteristics and study variables are

Varibales	Tamsulosin	Silodosin	p-value	
Body Mass index	Normal	72(43.4%)	94(56.6%)	0.730
	obese	5 (38.5%)	08(61.5%)	
Laterality	Right	65(55.6%)	52(44.4%)	0.001
	Left	12(19.4%)	50(80.6%)	
Symp To CT	Less than 1 week	67(64.4%)	37(35.6%)	
	More than 1 week	10(15.2%)	56(84.8%)	0.001
	More than 2 week	0 (0.0%)	09(100%)	
Posl n Ureler	Proximal	28(51.9%)	26(48.1%)	

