The side effects that patients using silodosin and tamsulosin experienced are analyzed in the table, and the p-value denotes the statistical significance of these data. Patients on Silodosin, with no side effects were 59.9% while 40.1% on Tamsulosin did not report any side effects. This implies that, in comparison to Tamsulosin, Silodosin may have a marginally higher correlation with patients reporting no adverse effects.

Examining particular side effects reveals various themes. Nine patients on tamsulosin (60.0%) and six patients on silodosin (40.0%) developed orthostatic hypotension, a condition marked by a considerable drop in blood pressure upon

standing. It suggested that Tamsulosin users are more likely to have orthostatic hypotension than Silodosin users.

Only a very tiny percentage of patients reported abnormal ejaculation; 2 individuals on tamsulosin (66.7%) and 1 patient on silodosin (33.3%). Again, this points to an increased chance of this specific adverse effect in Tamsulosin users.

[figure not shown]
Another side effect that was identified involved headaches, which were seen by 4 individuals on silodosin (44.4%) and 5 patients on tamsulosin (55.6%). Headaches were marginally more common among Tamsulosin users compared to Silodosin users, similar to orthostatic hypotension.

None of the detected differences in side effect distribution between Tamsulosin and Silodosin is statistically significant, according to the p-value of 0.315. This implies that even if there are discernible variations in the frequency of particular adverse effects between the two drugs, these variations might just be the result of random variation rather than an actual distinction in the side effect profiles of tamsulosin and silodosin.

In conclusion, the analysis of side effects reveals that patients taking silodosin have a tendency to report no side effects more often than individuals taking tamsulosin. On the other hand, it seems that tamsulosin users are more likely to experience certain adverse effects, like headache, orthostatic hypotension, and abnormal ejaculation. Even with these findings, the absence of statistical significance suggests that more investigation using larger sample sizes would be necessary to conclusively identify any significant variations in the side effect profiles of Tamsulosin and Silodosin.

Figure 2

Bar Chart showing comparison of stone expulsion rate in Tamsulosin and

Silodosin groups

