Similar results were seen in another study showing that, individuals receiving just tamsulosin treatment needed a greater average analgesic dosage of 391.43 \pm 165.60 mg with a p-value of 0.005, which denotes substantial significance, the necessary(50).

Similarly, a study showed statistically significant difference in the amount of analgesics needed by patients treated with Silodosin compared to those treated with tamsulosin only. The robustness of the conclusion was highlighted by the fact that the group receiving Silodosin treatment required considerably fewer analgesics than the groups receiving Tamsulosin, with a p-value of < 0.001(51).

Conclusion

An effective treatment for ureteral stones is medical expulsive therapy. According to our findings, silodosin has a safer profile and is more successful than tamsulosin at ejecting ureteric stones.

Silodosin had an increased rate of stone expulsion and took less time in stone expulsion compared to those treated with Tamsulosin.

In addition, patients treated with silodosin reported fewer side effects, such as a retrograde ejaculation, orthostatic hypotension and headaches as compared to those taking Tamsulosin.

In addition, those who received Silodosin needed less analgesic medication than those who received Tamsulosin.

•

REFERENCES

- Ahmed AFAM, Al-Sayed AYS. Tamsulosin versus Alfuzosin in the Treatment of Patients with Distal Ureteral Stones: Prospective, Randomized, Comparative Study. Korean J Urol. 2010 Mar;51(3):193–7.
- 5. Pietropaolo A, Proietti S, Geraghty R, Skolarikos A, Papatsoris A, Liatsikos E, et al. Trends of 'urolithiasis: interventions, simulation, and

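### The abstract and Conclusion claim that silodosin is safer, although the only side-effect test gives p = 0.315 and the Results call it non-significant

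*Combined protocol and SAP*

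**What the plan says.** The Objectives section lists as an aim "To compare the side effect profile of tamsulosin and silodosin when given for medical expulsive therapy". The alternative hypothesis covers safety as well as efficacy: "Silodosin is better than Tamsulosin in efficacy and safety". The Data Analysis Procedure sets the threshold: "P-value of less than 0.05 will be considered significant". It names a t-test and does not say whether tests are one- or two-sided.

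The Results report one side-effect test, on the table of side effects by drug (the second of two tables numbered 2). Of it the text says: "None of the detected differences in side effect distribution between Tamsulosin and Silodosin is statistically significant, according to the p-value of 0.315". It adds that "these variations might just be the result of random variation rather than an actual distinction in the side effect profiles", and that larger samples would be needed to settle the matter.

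The abstract's results paragraph nevertheless credits silodosin with success "in producing lesser side effects and hence better safety profile than Tamsulosin". The Conclusion says that "silodosin has a safer profile and is more successful than tamsulosin at ejecting ureteric stones" and presents this as a finding of the study. Neither place mentions the test or its result.

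**The concern.** The two headline statements assert what the Results section says was not shown. The test is not at fault; the inference drawn from it is. It is true of this sample that fewer side effects were recorded on silodosin. The step from there to a better safety profile is a claim about the drugs, and the trial's one test of that claim does not support it.

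Safety is a named objective and half of the alternative hypothesis, so this is a main conclusion. Anyone who reads only the abstract or the Conclusion would take a safety difference between the two drugs as established.

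A secondary problem makes misreading easier. The percentages beside each side effect (60.0% and 40.0% for orthostatic hypotension, for example) are each drug's share of the affected patients. They are not risks per arm, although they look like risks.

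**Working it through.** **Inputs.** All counts come from the side-effect table. They are treated as one category per patient, since the columns add up to the analysed total.

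| | Tamsulosin | Silodosin |
|---|---|---|
| None | 61 | 91 |
| Orthostatic hypotension | 9 | 6 |
| Abnormal ejaculation | 2 | 1 |
| Headache | 5 | 4 |
| Total | 77 | 102 |

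77 + 102 = 179, the analysed total stated in the Results. The pie chart's 43% and 57% equal 77/179 and 102/179.

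**1. Reproduce the reported p-value.** Pearson chi-square = sum of (observed - expected)²/expected, with expected = row total × column total / 179. Expected counts (tamsulosin, silodosin) are:

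- none: 65.39, 86.61
- orthostatic hypotension: 6.45, 8.55
- abnormal ejaculation: 1.29, 1.71
- headache: 3.87, 5.13

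The sum is 3.543 on 3 df, p = 0.3152. This matches the 0.315 in the text; the table prints 0.3.15, evidently a slip. Three of the eight expected counts are below 5, so exact versions were also run. Freeman-Halton gives p = 0.322 and the exact chi-square gives p = 0.333. Sparse cells do not explain the result.

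**2. Any listed side effect against none (post hoc).** Tamsulosin 9 + 2 + 5 = 16 of 77 (20.8%); silodosin 6 + 1 + 4 = 11 of 102 (10.8%).

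- Risk difference: 0.2078 - 0.1078 = 0.0999, or 10.0 points.
- Standard error: √(0.2078 × 0.7922/77 + 0.1078 × 0.8922/102) = 0.0555.
- 95% Wald interval: 10.0 ± 1.96 × 5.55 = -0.9 to 20.9 points. Newcombe: -0.7 to 21.3.
- Risk ratio: 0.2078/0.1078 = 1.93. SE of its log: √(1/16 - 1/77 + 1/11 - 1/102) = 0.361. 95% interval 0.95 to 3.91.

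| Test | Two-sided p | One-sided p |
|---|---|---|
| Pearson chi-square | 0.064 | 0.032 |
| t-test on 0/1 data | 0.065 | 0.032 |
| Fisher | 0.090 | 0.051 |

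**3. Single side effects.**

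- Orthostatic hypotension: 9/77 (11.7%) against 6/102 (5.9%), difference 5.8 points (Wald -2.7 to 14.3), two-sided Fisher p = 0.18.
- Headache: 5/77 (6.5%) against 4/102 (3.9%), difference 2.6 points (Wald -4.1 to 9.2), two-sided Fisher p = 0.50.
- Abnormal ejaculation: 2 against 1. The number of men per arm is not given, so no risk is computed.

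**4. Printed shares against risks.** For orthostatic hypotension the printed gap is 60.0 - 40.0 = 20 points, against 5.8 points per arm. The printed ratio is 60.0/40.0 = 1.5, against 11.7/5.9 = 1.99 per arm (from unrounded risks). For headache the printed ratio is 55.6/44.4 = 1.25, against 1.66 per arm. The printed shares therefore exaggerate the gap and understate the ratio.

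**5. Denominators.** The abstract gives 89 and 93 patients out of 180, but 89 + 93 = 182. The silodosin column alone has 91 + 11 = 102 patients, which cannot fit into 93. The calculations above therefore use 77 and 102.

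**The case against.** The strongest case has four parts.

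*The reported test is not the most direct one.* It looks for any difference across four categories on 3 df, whereas the claim is about fewer side effects overall. The alternative hypothesis is directional and the plan does not fix sidedness. A one-sided any-versus-none comparison gives 0.032 by chi-square or t-test. This is fair as far as it goes, but the contrast was neither planned nor reported, the one-sided results straddle 0.05 (Fisher 0.051), and the two-sided ones all exceed it. The authors themselves took 0.315 as their result and called it non-significant.

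*The body text already carries the caveat.* It does. The Results sentence saying that "it seems that tamsulosin users are more likely to experience certain adverse effects" is followed directly by a warning about the lack of significance. The Discussion concedes that the hypotension numbers are modest and the ejaculation numbers too small. Edits there are optional. The abstract and Conclusion, however, have no such caveat.

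*Analgesic need differed significantly (p = 0.005).* It is tabulated separately from side effects, which the Operational Definitions describe as undesirable effects after prescription of the drug. It cannot stand in for a side-effect test.

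*A per-arm table on 77 and 102 ignores missing patients.* This stands. If 104 were allocated to each arm, 27 tamsulosin and 2 silodosin patients are absent. With every missing outcome taken at its extreme, the observed difference could lie anywhere from 16/104 - 13/104 = 2.9 points to 43/104 - 11/104 = 30.8 points. The intervals above reflect sampling error among analysed patients only. This limits any new table, but does not support the headline wording.

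**Conclusion.** The concern holds. The abstract and Conclusion state a safety advantage that the trial's only side-effect test (p = 0.315, reproduced) does not support and that its own Results section declines to draw.

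The observed excess on tamsulosin is 10.0 points for any listed side effect, with a 95% interval from -0.9 to 20.9. The data are compatible with no difference and with a sizeable one, so neither superiority nor equal safety is shown.

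The p-value of 0.315 rests on the printed counts alone. The per-arm figures also assume that the arm sizes are 77 and 102 and that each patient falls in one category, and they describe analysed patients only. Reading the threshold as two-sided is an assumption, because the plan does not say. The fault is one of interpretation and must be corrected in the two headline statements.

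**What to change.** **Required.** In the abstract and the Conclusion, replace the safety claim with wording such as: fewer side effects were observed on silodosin; no difference in safety was demonstrated (p = 0.315 for the distribution of side effects); this does not show that the two drugs are equally safe. This rewords two sentences and makes the safety conclusion less favourable to silodosin. It needs no new data or analysis.

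**Optional, for consistency.** Bring the Results and Discussion sentences that describe tamsulosin users as being at higher risk of particular side effects into line with the same wording.

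**Secondary.** Replace the row shares with risks per arm, risk differences and 95% intervals on 77 and 102. Label them as analysed patients and show the missing patients by arm. Give abnormal ejaculation as counts, and mark any composite as post hoc. All the risks come from counts already printed.

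**Separate correction.** Reconcile the abstract's 89 and 93 out of 180 with the 77 and 102 used in the results tables. This needs a check against the participant flow record. Side-effect risks should not be computed on 89 and 93.

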Only a very tiny percentage of patients reported experiencing abnormal ejaculation; 2 individuals on tamsulosin (66.7%) and 1 patient on silodosin (33.3%) reported this side event. Again, this points to an increased chance of this specific adverse effect in Tamsulosin users, but the numbers are too low to make any firm conclusions. Another side effect that was identified involved headaches, which were seen by 4 individuals on silodosin (44.4%) and 5 patients on tamsulosin (55.6%). Headaches were marginally more common among Tamsulosin users compared to Silodosin users, similar to orthostatic hypotension.

Many urologists agree when it comes to the incidence of retrograde ejaculation that it is an indication of therapy efficacy rather than a negative effect. It seems that silodosin relaxes the smooth muscles in the genital and lower urinary tracts sufficiently to cause a retrograde ejaculation. Retrograde ejaculation was more common in the individuals who experienced the most alleviation from lower urinary tract symptoms, which was consistent with this conclusion. This finding implies that the retrograde ejaculation is, in fact, a passive marker of the smooth muscle relaxation brought on by silodosin(32).

Typically, nonselective $\alpha 1$ adrenoceptor antagonists such doxazosin and terazosin are linked to orthostatic hypotension. Nonetheless, in clinical trials, silodosin was linked to a modest incidence of orthostatic hypotension. According to the combined analysis of the US and European studies, 1.1% of patients receiving a placebo and 1.3% of patients receiving silodosin experienced orthostatic hypotension(48).

When compared to Tamsulosin, Silodosin is linked to a larger incidence of retrograde ejaculation but a reduced incidence of peripheral vasodilation-related adverse effects, such as orthostatic hypotension and dizziness, according to a retrospective review conducted by Imperatore et al(49).

In our study comparing the effects of Tamsulosin and Silodosin on patients, it was discovered that only 38.1% of those receiving Silodosin needed analgesics to ameliorate ureteric pain. On the other hand, 61.9% of patients receiving Tamsulosin required analgesic intervention, which is a far larger percentage. This significant difference raises the possibility that silodosin is more successful in treating ureteric stones and it also lowers their need for extra painkillers.

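### The Conclusion claims less retrograde ejaculation on silodosin, but the trial reports only abnormal ejaculation, at 2 v 1 events, too few to compare

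*Combined protocol and SAP*

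**What the plan says.** The side-effect entry under Operational Definitions is an open list: "including but not limited to abnormal ejaculation, headache, orthostatic hypotension, backache and gastritis etc". It names abnormal ejaculation but does not define it.

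The side-effect table has four rows: none, orthostatic hypotension, abnormal ejaculation and headache. The Results text reads: "Only a very tiny percentage of patients reported abnormal ejaculation; 2 individuals on tamsulosin (66.7%) and 1 patient on silodosin (33.3". These percentages are shares of the three events, not rates within an arm. The Abstract and the Discussion repeat the same counts under the same term. The Discussion adds that they are too small for a firm conclusion. The Results give p = 0.315 for the whole table and say that none of the side-effect differences is significant.

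The Conclusion then changes the term and drops both caveats: "patients treated with silodosin reported fewer side effects, such as a retrograde ejaculation, orthostatic hypotension and headaches as compared to those taking Tamsulosin".

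Elsewhere, retrograde ejaculation appears only as background on the drugs or in accounts of other studies. The Discussion reports one retrospective review in which, compared with tamsulosin, "Silodosin is linked to a larger incidence of retrograde ejaculation but a reduced incidence of peripheral vasodilation-related adverse effects". The Literature Review (Side effects) cites two meta-analyses: one of five randomised trials with no significant difference in retrograde ejaculation, and a larger one with more of it on silodosin.

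**The concern.** The Conclusion names a specific safety advantage that has no matching count in the trial. Of the three effects in the sentence, orthostatic hypotension and headache each have a row in the table, and retrograde ejaculation has none.

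The choice of word matters because none of the silodosin-tamsulosin comparisons of retrograde ejaculation that the document cites shows fewer events on silodosin. A prescriber who reads only the Conclusion could take the trial as evidence that silodosin lowers this risk. The trial reports three events of a differently named effect and, in its own Discussion, declines to conclude from them.

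**Working it through.** **Inputs.** The side-effect table gives these counts.

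| Row | Tamsulosin | Silodosin |
|---|---|---|
| None | 61 | 91 |
| Orthostatic hypotension | 9 | 6 |
| Abnormal ejaculation | 2 | 1 |
| Headache | 5 | 4 |
| Sum | 77 | 102 |

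The sums give 77 + 102 = 179, the analysed total in the Results. As tabulated, the four rows account for every analysed patient, and none of them is retrograde ejaculation. The Abstract gives different arm sizes (89 and 93). I use the table's own totals; with the Abstract's the rates would be 2/89 = 2.2% and 1/93 = 1.1%, in the same direction.

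**Step 1: reproduce the stated p-value.** Pearson chi-square is the sum of (observed - expected)²/expected, where expected = row total × column total / 179. The contributions, tamsulosin then silodosin, are:

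- none: 0.294 + 0.222
- orthostatic hypotension: 1.006 + 0.759
- abnormal ejaculation: 0.390 + 0.295
- headache: 0.329 + 0.248

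The sum is 3.543 on 3 degrees of freedom, p = 0.315, as stated. Three of the eight expected counts are below 5 (1.29, 1.71 and 3.87), but the likelihood-ratio version gives nearly the same result, p = 0.319.

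**Step 2: test the row behind the claim.** The rates are 2/77 = 2.6% and 1/102 = 1.0%, a difference of 1.6 points (95% Newcombe interval -3.1 to +8.1). For Fisher's exact test, the probability that k of the 3 events fall on tamsulosin is C(77,k) × C(102,3-k) / C(179,3), with C(179,3) = 939,929:

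- k = 0: 171,700 / 939,929 = 0.183
- k = 1: 396,627 / 939,929 = 0.422
- k = 2 (observed): 298,452 / 939,929 = 0.318
- k = 3: 73,150 / 939,929 = 0.078

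The two-sided p adds the outcomes no more probable than the one observed: (171,700 + 298,452 + 73,150) / 939,929 = 0.58.

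**Step 3: the other effects in the sentence.** Fisher p-values are 0.18 for orthostatic hypotension (9/77 = 11.7% v 6/102 = 5.9%), 0.50 for headache (5/77 = 6.5% v 4/102 = 3.9%) and 0.09 for any side effect (16/77 = 20.8% v 11/102 = 10.8%). None reaches the plan's 0.05 level.

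**Step 4: denominators.** Only men are at risk of an ejaculation effect. The Results say "In our study there are total 179 patients out of which 74 are females (41.3%) and 105 males (58.7"%), but do not give sex by arm. With m men on tamsulosin and 105 - m on silodosin, the silodosin rate is lower when 1/(105 - m) < 2/m, that is, when m < 70. As an assumed example, m = 45 gives 2/45 = 4.4% v 1/60 = 1.7%, Fisher p = 0.58. The rates tie at m = 70 and reverse only from 71 of the 77 upwards. Male denominators change the rates; the comparison still rests on three events.

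**The case against.** The best defence is that this is loose vocabulary. The Conclusion's three effects match the table's three named rows one to one. The Discussion gives a list of tamsulosin side effects close to the one under Operational Definitions, with retrograde in place of abnormal ejaculation, and it passes soon from the trial's ejaculation count to remarks on retrograde ejaculation. The definition is an open list, so it does not bar reporting a retrograde event. The report also discloses, outside the Conclusion, that the counts are small and the differences not significant.

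Much of this stands, and inconsistent terminology is a likely explanation. It does not rescue the sentence. No section says that the three events were retrograde, and under either label 2 v 1 cannot support a claim of fewer.

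Four stronger readings are tempting, and the documents do not support them:

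- A reader might infer that the change of term could reverse the direction. Relabelling leaves 2 v 1. If the retrograde events were an unknown subset of the three, there would be six possible splits. With 77 and 102 as denominators, four favour silodosin, one is a tie (0 v 0) and one reverses (0 v 1, Fisher p = 1.0). Nothing points to that last split.
- A reader might put limits on the retrograde difference from these splits. The denominators of 77 and 102 include women, and men by arm are not given, so such limits would not be valid.
- A reader might infer that all the cited evidence runs against silodosin. It is mixed: the five-trial meta-analysis found no significant difference.
- A reader might infer that retrograde ejaculation was never measured. The documents show only that it was not reported separately.

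**Conclusion.** Wrong as written. The Conclusion claims a reduction in an effect for which the trial gives no count. The nearest reported effect, abnormal ejaculation, occurred in 2/77 v 1/102 patients (Fisher p = 0.58; difference 1.6 points, 95% interval -3.1 to +8.1), which shows neither a benefit nor a harm. The same sentence presents side effects as fewer on silodosin without repeating the report's own finding of no significant difference (p = 0.315).

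The arm totals are taken from the table, and the rates use all patients because sex by arm is not reported. The verdict does not depend on either choice. No count or test in the report needs to change; the fault is in what the Conclusion draws from them.

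**What to change.** In the Conclusion:

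- Remove retrograde ejaculation from the effects said to be fewer on silodosin. State instead, for example: *Abnormal ejaculation was reported by 2 patients on tamsulosin and 1 on silodosin, too few to compare.* Give the number of men in each arm as the denominator.
- State that retrograde ejaculation was not reported separately. If the trial records identify such events, give the counts by arm instead.
- State that no difference in side effects was shown (p = 0.315), so that the wording on orthostatic hypotension, headache and overall safety agrees with the Results.

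The cost is a few sentences and a cross-tabulation of sex by arm from data already held. The safety conclusion becomes less favourable to silodosin.
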